13.7.8. Health Outcome Analyses

Symptom impact and HRQoL will be assessed using the e-Diary. Change from baseline and change over time will be summarized.

The calculation of scores and methods to deal with missing data will be provided in the RAP.

Visual Functioning Questionnaire (NEI VFQ-25 and OSDI): Data will be collected from end of treatment (EOT) visit as baseline. Additional data will be collected in follow-up visits on a monthly basis for subjects with ongoing corneal events or signs at EOT for 1 year or until resolution, whichever occurs first. These data will not be collected for subjects who already completed the treatment. Methods for calculation of scores will be provided in the RAP. Due to limited number of on-treatment subjects at the time of protocol amendment, only individual subject data will be presented.

14. STUDY CONDUCT CONSIDERATIONS

14.1. Posting of Information on Clinicaltrials.gov

Study information from this protocol will be posted on publicly available clinical trial registers before enrolment of subjects begins.

14.2. Regulatory and Ethical Considerations, Including the Informed Consent Process

Prior to initiation of a study site, GSK will obtain approval from the appropriate regulatory agency to conduct the study in accordance with International Conference on Harmonization Good Clinical Practice (ICH GCP) and applicable country-specific regulatory requirements.

The study will be conducted in accordance with all applicable regulatory requirements.

The study will be conducted in accordance with ICH GCP, all applicable subject privacy requirements, and the ethical principles that are outlined in the Declaration of Helsinki 2008, including, but not limited to:

- Institutional review board (IRB)/ethics committee (EC) review and approval of study protocol and any subsequent amendments
- Subject informed consent
- Investigator reporting requirements

GSK will provide full details of the above procedures, either verbally, in writing, or both.

Written informed consent must be obtained from each subject prior to participation in the study.

14.3. Urgent Safety Measures

If an event occurs that is related to the conduct of the study or the development of the IP, and this new event is likely to affect the study of subjects, the Sponsor, and the investigator will take appropriate urgent safety measures to protect subjects against any immediate hazard.

The Sponsor will work with the investigator to ensure the Institutional review board (IRB)/ethics committee (EC) is notified.

14.4. Quality Control (Study Monitoring)

In accordance with applicable regulations, Good Clinical Practice (GCP) and GSK procedures, the site will be contacted prior to the start of the study to review with the site staff the protocol, study requirements, and their responsibilities to satisfy regulatory, ethical, and GSK requirements. When reviewing data collection procedures, the discussion will include identification, agreement and documentation of data items for which the electronic case report form (eCRF) will serve as the source document.

The investigator and the head of the medical institution (where applicable) agrees to allow the monitor direct access to all relevant documents and to allocate their time and the time to their staff to monitor to discuss findings and any issues.

Monitoring visits will be conducted in a manner to ensure that the:

- Data are authentic, accurate, and complete.
- Safety and rights of subjects are being protected.
- Study is conducted in accordance with the currently approved protocol and any other study agreements, ICH GCP, and all applicable regulatory requirements.

14.5. Quality Assurance

To ensure compliance with International Conference on Harmonization Good Clinical Practice (ICH GCP) and all applicable regulatory requirements, GSK may conduct quality assurance audits of the site. Regulatory agencies may conduct a regulatory inspection at any time during or after completion of the study. In the event of an audit or inspection, the investigator (and institution) must agree to grant the auditor(s) and inspector(s) direct access to all relevant documents and to allocate their time and the time of their staff to discuss any findings/relevant issues.

14.6. Study and Site Closure

The end of the study will be defined as the date of the last visit of the last subject enrolled.

Upon completion or termination of the study, the monitor will conduct site closure activities with the investigator or site staff (as appropriate), in accordance with applicable regulations, International Conference on Harmonization Good Clinical Practice (ICH GCP), and GSK Standard Operating Procedures.

GSK reserves the right to temporarily suspend or terminate the study at any time for reasons including (but not limited to) safety issues, ethical issues, or severe noncompliance. If GSK determines that such action is required, GSK will discuss the reasons for taking such action with the investigator or head of the medical institution (where applicable). When feasible, GSK will provide advance notice to the investigator or head of the medical institution of the impending action.

If a study is suspended or terminated for safety reasons, GSK will promptly inform all investigators, heads of the medical institutions (where applicable), and/or institutions conducting the study. GSK will also promptly inform the relevant regulatory authorities of the suspension/termination along with the reasons for such action. Where required by applicable regulations, the investigator or head of the medical institution must inform the IRB/EC promptly and provide the reason(s) for the suspension/termination.

GSK may also close study sites which fail to recruit subjects within a predefined timeframe, as defined within the Study Procedures Manual (SPM).

14.7. Records Retention

Following closure of the study, the investigator or head of the medical institution (where applicable) must maintain all site study records (except for those required by local regulations to be maintained elsewhere) in a safe and secure location. The records must be easily accessible when needed (e.g., for a GSK audit or regulatory inspection) and must be available for review in conjunction with assessment of the facility, supporting systems, and relevant site staff.

Where permitted by local laws/regulations or institutional policy, some or all of the records may be maintained in a format other than hard copy (e.g., microfiche, scanned, electronic); however, caution must be exercised before such action is taken. The investigator must ensure that all reproductions are legible and are a true and accurate copy of the original. In addition, they must meet accessibility and retrieval standards, including regeneration of a hard copy, if required. The investigator must also ensure that an acceptable back-up of the reproductions exists and that there is an acceptable quality control procedure in place for creating the reproductions.

GSK will inform the investigator of the time period for retaining the site records in order to comply with all applicable regulatory requirements. The minimum retention time will meet the strictest standard applicable to a particular site, as dictated by local laws/regulations, GSK standard operating procedures, and/or institutional requirements.

The investigator must notify GSK of any changes in the archival arrangements, including, but not limited to archival of records at an off-site facility or transfer of ownership of the records in the event that the investigator is no longer associated with the site.

14.8. Provision of Study Results to Investigators, Posting of Information on Publicly Available Clinical Trials Registers and Publication

Where required by applicable regulatory requirements, an investigator signatory will be identified for the approval of the clinical study report. The investigator will be provided reasonable access to statistical tables, figures, and relevant reports and will have the opportunity to review the complete study results at a GSK site or other mutually-agreeable location.

GSK will also provide the investigator with the full summary of the study results. The investigator is encouraged to share the summary results with the study subjects, as appropriate.

The results summary will be posted to the GSK Clinical Study Register no later than eight months after the final primary completion date, the date that the final subject was examined or received an intervention for the purposes of final collection of data for the primary outcome. In addition, a manuscript will be submitted to a peer reviewed journal for publication no later than 18 months after the last subject's last visit (LSLV). When manuscript publication in a peer reviewed journal is not feasible, a statement will be added to the register to explain the reason for not publishing.

16. APPENDICES

16.1. Appendix 1: International Myeloma Working Group Uniform Response Criteria for Multiple Myeloma

Response	IMWG Criteria
sCR	
 CR as defined below plus normal FLC ratio and absence of clonal cells in bone marrow³ by immunohistochemistry or immunofluorescence⁴
CR	
 Negative immunofixation on the serum and urine and disappearance of any soft tissue plasmacytomas and < 5% plasma cells in bone marrow³
VGPR	
 Serum and urine M-protein detectable by immunofixation but not on electrophoresis 
or
 
 ≥ 90% reduction in serum M-protein plus urine M-protein level <100 mg/24 h
PR	
 ≥ 50% reduction of serum M-protein and reduction in 24 hours urinary M-protein by ≥90% or to < 200 mg/24 h If the serum and urine M-protein are unmeasurable,⁵ a ≥ 50% decrease in the difference between involved and uninvolved FLC levels is required in place of the M-protein criteria If serum and urine M-protein are not measurable, and serum free light assay is also not measurable, ≥ 50% reduction in plasma cells is required in place of M-protein, provided baseline bone marrow plasma cell percentage was ≥ 30% In addition to the above listed criteria, if present at baseline, a ≥ 50% reduction in the size of soft tissue plasmacytomas is also required
MR	
 ≥25% but <49% reduction of serum M protein and reduction in 24 hour urine M protein by 50-89%, which still exceeds 200 mg per 24 hour In addition to the above criteria, if present at baseline, 25-49% reduction in the size of soft tissue plasmacytomas is also required No increase in size or number of lytic bone lesions (development of compression fracture does not exclude response)
No change/Stable disease	
 Not meeting criteria for CR, VGPR, PR, or progressive disease
Progressive Disease	
 Increase of ≥ 25% from lowest response value in any one or more of the following: 
 ○ Serum M-component and/or (the absolute increase must be ≥ 0.5 g/dL)⁶ ○ Urine M-component and/or (the absolute increase must be ≥200 mg/24 h)

Response	IMWG Criteria
	
 • Only in patients without measurable serum and urine M-protein levels; the difference between involved and uninvolved FLC levels. The absolute increase must be > 10 mg/dL • Bone marrow plasma cell percentage; the absolute percentage must be $\geq 10\%$⁷ • Definite development of new bone lesions or soft tissue plasmacytomas or definite increase in the size of existing bone lesions or soft tissue plasmacytomas • Development of hypercalcaemia (corrected serum calcium > 11.5 mg/dL or 2.65mmol/L) that can be attributed solely to the plasma cell proliferative disorder
Relapse	
Clinical relapse requires one or more of:
 
 • Direct indicators of increasing disease and/or end organ dysfunction (CRAB features).⁶ It is not used in calculation of time to progression or progression-free survival but is listed here as something that can be reported optionally or for use in clinical practice • Development of new soft tissue plasmacytomas or bone lesions • Definite increase in the size of existing plasmacytomas or bone lesions. A definite increase is defined as a 50% (and at least 1 cm) increase as measured serially by the sum of the products of the cross-diameters of the measurable lesion • Hypercalcemia (> 11.5 mg/dL) [2.65 mmol/L] • Decrease in haemoglobin of ≥ 2 g/dL [1.25 mmol/L] • Rise in serum creatinine by 2 mg/dL or more [177 mol/L or more]
Relapse from CR⁵ (to be used only if the endpoint studied is DFS)⁸	
Any one or more of the following:
 
 • Reappearance of serum or urine M-protein by immunofixation or electrophoresis • Development of $\geq 5\%$ plasma cells in the bone marrow⁷ • Appearance of any other sign of progression (i.e., new plasmacytoma, lytic bone lesion, or hypercalcaemia)

Overall Responders: PR, VGPR, CR, sCR

Clinical Benefit Rate: Overall responders + MR

Adapted from Durie BGM, et al. Leukemia 2006; 20: 1467-1473; and Kyle RA, Rajkumar SV. Leukemia 2008;23:3-9.

Note: A clarification to IMWG criteria for coding CR and VGPR in patients in whom the only measurable disease is by serum FLC levels: CR in such patients is defined as a normal FLC ratio of 0.26–1.65 in addition to CR criteria listed above. VGPR in such patients is defined as a >90% decrease in the difference between involved and uninvolved free light chain (FLC) levels.
 3 Confirmation with repeat bone marrow biopsy not needed.

4 Presence/absence of clonal cells is based upon the kappa/lambda ratio. An abnormal kappa/lambda ratio by immunohistochemistry and/or immunofluorescence requires a minimum of 100 plasma cells for analysis. An abnormal ratio reflecting presence of an abnormal clone is kappa/lambda of $> 4:1$ or $< 1:2$.

5 All relapse categories require two consecutive assessments made at any time before classification as relapse or disease progression and/or the institution of any new therapy. In the IMWG criteria, CR patients must also meet the criteria for progressive disease shown here to be classified as progressive disease for the purposes of calculating time to progression and progression-free survival. The definitions of relapse, clinical relapse and relapse from CR are not to be used in calculation of time to progression or progression free survival

6 For progressive disease, serum M-component increases of ≥ 1 gm/dL are sufficient to define relapse if starting M-component is ≥ 5 g/dL.

7 Relapse from CR has the 5% cut-off versus 10% for other categories of relapse.

8 For purposes of calculating time to progression and progression-free survival, CR patients should also be evaluated using criteria listed above for progressive disease.

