5.2. Subject Selection Criteria

5.2.1. Inclusion Criteria

Specific information regarding warnings, precautions, contraindications, adverse events (AEs), and other pertinent information on the GSK study treatment that may impact subject eligibility is provided in the Investigator Brochure (IB)/IB supplement(s). Deviations from inclusion criteria are not allowed because they can potentially jeopardize the scientific integrity of the study, regulatory acceptability or subject safety. Therefore, adherence to the criteria as specified in the protocol is essential.

Subjects eligible for enrolment in the study must meet all of the following criteria:

1. Provide signed written informed consent, which includes compliance with the requirements and restrictions listed in the consent form
2. Male or female, 18 years or older (at the time consent is obtained)
3. Eastern Cooperative Oncology Group (ECOG) performance status of 0 or 1 ([Appendix 6](#))
4. **Part 1/dose escalation:**
 - Histologically or cytologically confirmed diagnosis of: Multiple Myeloma in a subject who fulfills **all** of the following:
 - has undergone stem cell transplant, or is considered transplant ineligible,
 - has been pretreated with at least the 3 following classes of anti-myeloma drugs: alkylators, proteasome inhibitors and immunomodulators,

- has demonstrated progression on, or within 60 days of completion of the last therapy.

Part 2 /MM cohort:

- Histologically or cytologically confirmed diagnosis of: Multiple Myeloma in a subject who fulfills **all** of the following:
- has undergone stem cell transplant, or is considered transplant ineligible,
- has been pretreated with at least the 3 following classes of anti-myeloma drugs: alkylators, proteasome inhibitors and immunomodulators,
- and has demonstrated progression on, or within 60 days of completion of the last therapy.
- AND has measurable disease with at least one of the following:
 - a. Serum M-protein ≥ 0.5 g/dL (≥ 5 g/L)
 - b. Urine M-protein ≥ 200 mg/24h
 - c. Serum FLC assay: Involved FLC level ≥ 5 mg/dL (≥ 50 mg/L) and an abnormal serum free light chain ratio (< 0.26 or > 1.65)
 - d. Biopsy proven plasmacytoma (should be measured within 28 days of Screening Visit)

or

Part 2/ BCMA positive Lymphoma cohort:

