29	Shaded	Shaded	Shaded	Shaded	Shaded	Shaded	Shaded						
30	Shaded	Shaded	Shaded	Shaded	Shaded	Shaded	Shaded						
31	Shaded	Shaded	Shaded	Shaded	Shaded	Shaded	Shaded						
32	Shaded	Shaded	Shaded	Shaded	Shaded	Shaded	Shaded	Shaded					
33	Shaded	Shaded	Shaded	Shaded	Shaded	Shaded	Shaded	Shaded	Shaded				
34	Shaded	Shaded	Shaded	Shaded	Shaded	Shaded	Shaded	Shaded	Shaded	Shaded			
35	Shaded	Shaded	Shaded	Shaded	Shaded	Shaded	Shaded	Shaded	Shaded	Shaded			
36	Shaded	Shaded	Shaded	Shaded	Shaded	Shaded	Shaded	Shaded	Shaded	Shaded			
37	Shaded	Shaded	Shaded	Shaded	Shaded	Shaded	Shaded	Shaded	Shaded	Shaded	Shaded		
38	Shaded	Shaded	Shaded	Shaded	Shaded	Shaded	Shaded	Shaded	Shaded	Shaded	Shaded		
39	Shaded	Shaded	Shaded	Shaded	Shaded	Shaded	Shaded	Shaded	Shaded	Shaded	Shaded	Shaded	
40	Shaded	Shaded	Shaded	Shaded	Shaded	Shaded	Shaded	Shaded	Shaded	Shaded	Shaded	Shaded	Shaded

Note: The shaded regions are the specific regions for stopping the study for futility. For instance, if there are 4-5 or fewer responses in 25 subjects, then the predictive probability for success will be less than the futility criterion, 5.0%, and the study will be stopped.

In addition to the considering the recommendations of the futility analyses, final decisions on stopping enrolment in the MM cohort will depend on the totality of the data collected. Examples of consideration of the totality of the data include, further investigation of the clinical activity of subgroups of subjects based on their BCMA expression levels and evaluation of the quality of responses (including sCR, CR and Clinical Benefit Rate, as defined in [Appendix 1](#)). Should the recommendation to stop for futility be disregarded in favor of a decision to continue the trial based on the totality of the data, the overall type I error rate of the expansion phase will be inflated.

No interim analyses will be performed on the BCMA+ lymphomas cohort; though consideration would be given to closing the cohort should the enrollment be stopped in the MM cohort.

If necessary, a subject may be replaced if they are deemed to be Lost to Follow-Up (LTFU) or they have withdrawn due to a toxicity deemed to not have been related to GSK2857916.

Subjects will not be replaced when they discontinue the study due to: Progression (symptomatic or otherwise), toxicity related to GSK2857916, or lack of efficacy.

Other administrative interim analyses may be performed if needed.

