13.7.7. Clinical Activity Analyses

Overall Response Rate (ORR) is one of the secondary endpoints to measure clinical activity of this study.

For multiple myeloma, ORR is defined as the percentage of subjects with a confirmed PR or better (i.e. PR, VGPR, CR and sCR), according to the IMWG Panel I ([Appendix 1](#)), as assessed by the investigator. In addition, Clinical Benefit rate (CBR) is defined as the percentage of subjects with a confirmed MR or better (i.e. MR, PR, VGPR, CR and sCR), according to the IMWG Panel I ([Appendix 1](#)), as assessed by the investigator.

The number and percentage of subjects in the following response categories will be presented sCR (stringent complete response), (complete response) CR, (very good partial response) VGPR, (partial response) PR, (minimal response) MR, stable disease (SD), progressive disease (PD), and not evaluable (NE)

sCR+CR+VGPR+PR for overall response (ORR)

sCR+CR+VGPR+PR+MR for Clinical Benefit rate (CBR)

The corresponding exact 95% CI for ORR and Clinical Benefit Rate (CBR) will also be provided. Subjects with unknown or missing response will be treated as non-responders, i.e., these subjects will be included in the denominator when calculating percentages of response.

For lymphoma, ORR is defined as the percentage of subjects with confirmed CR, or PR, as described in the Revised Response Criteria for Malignant Lymphoma ([Appendix 2](#)). ORR for lymphomas will be summarized in a similar way as multiple myeloma. The corresponding exact 95% CI for ORR will also be provided.

Other exploratory time-to-event (TTE) endpoints related to clinical activity for Part 2 (MM) of this study are TTP, DOR, TTR, and PFS.

Time to disease progression (TTP) is defined as the time from first dose until the earliest date of PD per IMWG, or death due to PD. Determination of dates of TTP event and dates for censoring will be described in the RAP. **Duration of response (DOR)** is defined as the time from first documented evidence of PR or better until disease progression (PD) per IMWG, or death due to PD among subjects who achieve a response

(i.e. confirmed PR or better). Responders without disease progression will be censored at the censoring time point for TTP.

Time to response (TTR) is defined as the time between the date of first dose and the first documented evidence of response (PR or better). Subjects without confirmed response (PR or better) will be censored at the censoring date for TTP.

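### Read literally, the minimal response (MR) row in Appendix 1 shuts out every subject with baseline urine M-protein of 400 mg/24 h or less and every FLC-only subject, and stable disease (SD) does not exclude MR

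*Protocol*

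**What the plan says.** Appendix 1 (Section 16.1) is the operative response table for myeloma.

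- **MR:** the M-protein condition is "≥25% but <49% reduction of serum M protein and reduction in 24 hour urine M protein by 50-89%, which still exceeds 200 mg", the last figure being a 24-hour amount. For plasmacytomas present at baseline, "25-49% reduction in the size of soft tissue plasmacytomas is also required". Lytic lesions must not have increased in size or number.
- **PR:** "≥ 50% reduction of serum M-protein and reduction in 24 hours urinary M-protein by ≥90% or to < 200 mg/24 h". If serum and urine are both unmeasurable, a 50% "decrease in the difference between involved and uninvolved FLC levels is required in place of the M-protein criteria". A further plasma-cell substitute follows. MR has no counterpart to any of these routes. The note under the table for subjects measurable only by FLC deals with CR and VGPR, not MR.
- **SD:** "Not meeting criteria for CR, VGPR, PR, or progressive disease".

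Section 5.2.1, criterion 4, for the Part 2 MM cohort reads "AND has measurable disease with at least one of the following" and lists serum M-protein, urine M-protein of at least 200 mg/24 h, FLC and biopsy-proven plasmacytoma.

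Section 13.7.7 states that "Clinical Benefit rate (CBR) is defined as the percentage of subjects with a confirmed MR or better" under Appendix 1, as judged by the investigator. It gives CBR an exact 95% CI and lists MR and SD as separate response categories. Section 13.6.2 names "evaluation of the quality of responses (including sCR, CR and Clinical Benefit Rate" among the examples of data that may inform the decision to stop MM enrolment.

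**The concern.** The entry rule and the MR rule do not fit together. A subject may enter on one marker, but MR asks for a defined fall in both serum and urine, with a sizeable amount of urine protein left over. PR avoids this problem through its alternative urine clause and its substitutes. As a result, a serum-only subject can be scored PR but never MR, and a subject whose urine responds very well can lose MR for that reason.

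CBR is ORR plus MR, so any subject wrongly barred from MR is missing from the CBR numerator. If some sites apply the table word for word and others judge only what was measurable, CBR also means different things at different sites. The SD definition adds a second problem: a subject who meets MR also meets SD, although the two are tabulated as distinct categories.

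**Working it through.** The protocol states no expected CBR or MR rate and no power for CBR, so there is no figure to reproduce. The check applies the Appendix 1 rows as logical rules, using the inputs quoted above.

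**Rules as written** (s = serum fall, f = urine fall, U0 = baseline urine in mg/24 h, residual = U0(1 − f))

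- PR: s ≥ 50%, and (f ≥ 90% or residual < 200).
- MR: 25% ≤ s < 49%, and 50% ≤ f ≤ 89%, and residual > 200.

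**Minimum baseline urine for MR:** U0 > 200/(1 − f)

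| Urine fall f | U0 must exceed |
|---|---|
| 50% | 200/0.50 = 400 |
| 75% | 200/0.25 = 800 |
| 89% | 200/0.11 = 1818 |

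The smallest bound is 400 mg/24 h, so nobody at or below it can be MR. A grid over all serum falls, baseline urine from 0 to 400 mg/24 h and all urine falls found no qualifying cell. Serum-only subjects (urine below 200) lie wholly inside this region. So do FLC-only subjects, for whom the MR row offers no substitute.

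**Contrast with PR:** at U0 = 100 with no urine change, s = 50% is PR because the residual is below 200. At s = 40% the same subject cannot be MR.

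**Boundary and discordant cases**

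| Case | PR? | MR? | Falls to |
|---|---|---|---|
| Serum 2.00 to 1.01 g/dL, (2.00 − 1.01)/2.00 = 49.5%; urine 1000 to 400 | No, s < 50% | No, s ≥ 49% | SD |
| Serum −40%, urine −89.5% | No, s < 50% | No, f > 89% | SD |
| Serum −40%, urine 1000 to 80 (−92%) | No, s < 50% | No, f > 89% and residual < 200 | SD |
| Serum −40%, urine 600 to 180 (−70%) | No, s < 50% | No, residual < 200 | SD |
| Serum −60%, urine 1000 to 400 (−60%) | No, f < 90% and residual ≥ 200 | No, s ≥ 49% | SD |
| Serum −40%, urine 1000 to 400 (−60%) | No | Yes | MR, and also SD as worded |

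**Effect on CBR:** each lost MR removes 1/40 = 2.5 percentage points in a full cohort of 40. As an illustration, assume 16 of 40 subjects are PR or better:

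| MRs recovered | CBR | Exact 95% CI |
|---|---|---|
| 0 | 16/40 = 40.0% | 24.9–56.7 |
| 1 | 17/40 = 42.5% | 27.0–59.1 |
| 2 | 18/40 = 45.0% | 29.3–61.5 |
| 4 | 20/40 = 50.0% | 33.8–66.2 |

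The 16 responders and the numbers recovered are assumptions, not protocol figures.

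**The case against.** The best defence is that the table was never meant to be applied mechanically. Response is the investigator's assessment, and taken word for word even PR would fail for a urine-only subject, who would need a 50% fall in a serum protein that cannot be measured. The FLC substitute in PR also points to scoring on measurable components. An investigator who works that way would not lose these MRs. This stands in part: it means that a downward bias in the reported CBR is not demonstrated. But no sentence in the protocol says that MR is judged on the measurable component, and leaving this to each site makes CBR inconsistent across sites.

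Second, CBR is an add-on. The synopsis and Section 13.5.2 say only that it may be considered or explored, it has no hypothesis, and the futility rule uses ORR alone. This stands and limits the importance of the point. Section 13.7.7 nevertheless commits to a CBR with a confidence interval.

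Third, a reader might infer three stronger things that the documents do not support.

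- **That the gap cases have no category at all.** SD is the residual class and takes them; the harm is demotion from MR.
- **That the SD wording itself bars subjects from MR.** Response tables are hierarchical, and the overlap lowers CBR only if a subject who qualifies for both is coded SD.
- **That CBR is understated by a known amount.** If 60–80% of subjects were serum-only or FLC-only and the true MR rate were 10%, then of 0.10 × 40 = 4 MRs, 2.4 to 3.2 would be lost, or 6 to 8 points. Both inputs are assumed; the protocol gives neither.

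**Conclusion.** The point holds as a defect in a stated definition. Applied literally, MR is impossible for anyone with baseline urine M-protein of 400 mg/24 h or less and for every FLC-only subject, in a cohort that admits subjects on any single marker. Boundary and discordant cases drop to SD, and MR and SD are not mutually exclusive as worded although they are tabulated separately.

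The direction is clear: literal scoring can only remove subjects from MR, so it can only lower CBR, by 2.5 percentage points per lost MR in 40 subjects. The total is unknown, and it would be zero if every site judged only measurable components. ORR, its 20% versus 40% test and the Table 17 boundary do not depend on MR and are unaffected. The matter should be corrected, but it does not threaten the main activity conclusion.

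**What to change.** In Appendix 1:

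- Judge MR on each M-protein component measurable at baseline: a serum fall of at least 25% and a urine fall of at least 50%, not meeting PR. Remove the residual-urine floor and use no upper cut-off other than PR. This also resolves urine-only and discordant cases.
- For plasmacytomas present at baseline, require a reduction of at least 25%, and say that this applies to plasmacytoma-only subjects too.
- Keep the lytic-lesion condition.
- State explicitly whether FLC-only subjects have an MR route. If they do not, report CBR with that limitation.
- Add MR to the categories that SD excludes.

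The cost is one table, a clarification to sites, and re-derivation of MR and SD from data already collected. M-protein and FLC are scheduled at each cycle start from Cycle 2. Plasmacytoma imaging is less frequent (screening, Cycles 5, 9 and 13, and end of treatment), so that component can be re-scored only at those times.

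The study is open-label, and Section 13.7.8 notes that few subjects were still on treatment at the amendment, so most responses may already be known. A change that can only raise CBR should therefore be shown beside CBR under the present Appendix 1 wording.
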